11 ASSESSMENT OF EFFICACY AND HEALTH OUTCOMES VARIABLES

11.1 PedACR30, PedACR50, PedACR70, and PedACR90 clinical response

The PedACR30, PedACR50, PedACR70, and PedACR90 clinical responses rates (Giannini et al, 1997; Lovell et al, 2008) at every visit compared to Baseline (except the Final Visit) will be assessed. The assessments are based on a 30%, 50%, 70%, and 90% or greater improvement in at least 3 of the 6 core set measures with no more than 1 of the remaining worsened by >30%. The 6 core set measures are:

- Number of joints with active arthritis (joints with swelling not due to deformity or inactive synovitis, or joints with limitation of motion with pain, tenderness, or both)
- Number of joints with limitation of range of motion
- Physician's Global Assessment of Disease Activity (VAS)
- CHAQ completed by parent or caregiver (Appendix 17.1)
- Parent's Global Assessment of Overall Well-Being (VAS) (Appendix 17.3)
- Acute phase reactant (CRP)

Documentation of the assessment of all 6 core set measures will be submitted to UCB or designee for immediate review of completeness at Week 0 (Baseline) and Week 24, while the study participant is still on site.

11.2 PRINTO/PRCSG standard joint examination

The following 75 joints are to be examined for swelling, pain on motion (POM), tenderness, and limitation of motion (LOM) by the Investigator, another delegated physician, or an appropriately qualified medical professional (based on local requirements) who has had documented training on how to perform these assessments correctly. Preferably the same assessor should evaluate the study participant at each arthritis assessment, as per PRINTO/PRCSG guidelines. The individual with this delegated duty must be listed on Form 1572.

- Upper body (6) - bilateral temporomandibular, sternoclavicular, and acromioclavicular joints
- Upper extremity (34) - bilateral shoulders, elbows, wrists, metacarpals (MCP I, II, III, IV, and V), proximal interphalangeals (PIP I, II, III, IV, and V) and distal interphalangeals (DIP II, III, IV, and V)
- Lower extremity (30) - bilateral hips, knees, ankles, subtalar, tarsi, metatarsophalangeals (MTP I, II, III, IV, and V), and proximal interphalangeals (PIP I, II, III, IV, and V)
- Spinal (5) – cervical spine, thoracic spine, and lumbar spine, and bilateral sacroiliac joints

The assessment for LOM is made on 69 joints from the above list. The sternoclavicular, acromioclavicular, and sacroiliac joints are excluded. The assessment for swelling is made on

66 joints from the above list. The hip, subtalar, cervical spine, thoracic spine, lumbar spine, and sacroiliac joints are excluded. Artificial and ankylosed joints are excluded from both tenderness and swelling assessments.

Joint assessment will be based on a 2-point scale as unaffected (Grade 0) and affected (Grade 1).

These assessments are completed at Screening, Baseline, and every visit (including Unscheduled Visits that are related to dose change) through the Early Discontinuation/End of Treatment Visit.

11.3 Number of joints with active arthritis and number of joints with limitation of range of motion

The change in the number of joints with active arthritis and the change in the number of joints with limitation of range of motion will be assessed. Joint and joint motion assessments will be performed as part of the PRINTO/PRCSG standard joint examination.

11.4 Physician's Global Assessment of Disease Activity (VAS)

The Investigator will assess the overall status of the study participant with respect to their JIA signs and symptoms and functional capacity using a 0 to 100mm VAS where 0 is "very good, asymptomatic and no limitation of normal activities" and 100 is "very poor, very severe symptoms which are intolerable and inability to carry out all normal activities."

The Physician's Global Assessment of Disease Activity (VAS) will be completed at Screening, Baseline, and every visit (including Unscheduled Visits that are related to dose change) through the Early Discontinuation/End of Treatment Visit.

11.5 Childhood Health Assessment Questionnaire (CHAQ)

The Childhood Health Assessment Questionnaire (CHAQ) is an adaptation of the Health Assessment Questionnaire-Disability Index (HAQ-DI), which is a questionnaire developed to assess physical function in adults (Singh et al, 1994). The CHAQ was developed specifically as a measure of function for children with juvenile RA and the population evaluated for the development of this questionnaire comprised study participants between ages 1 to 19 years old with JIA. The CHAQ is a parent/caregiver-reported questionnaire and the recall period is "the past week."

The disability section of the CHAQ uses 30 questions (5-point Likert scale) to assess 8 domains of daily living, namely dressing & grooming, arising, eating, walking, hygiene, reach, grip, and activities. In addition to the questions on activities of daily living, there are 14 questions relating to the use of aids or devices, and 8 questions concerning activities in which assistance of another person is required. The CHAQ for use in children differs from the HAQ-DI in that several new questions have been added such that for each functional area, there is at least 1 question that is relevant to children of all ages. Further, to eliminate discrepancies introduced by growth and development, parents/caregivers are asked to note only those difficulties that are caused by arthritis. The question with the highest score determines the score for that functional area. If aids or devices are used or help is needed to complete tasks in a certain area, a minimum score of 2 is recorded for the corresponding

functional area. The scores for each of the 8 functional areas or domains are averaged to calculate the Disability Index which yields a score of 0 representing “no disability” to 3 representing “very severe disability.”

A copy of the CHAQ is provided in Appendix 17.1. The CHAQ will be completed by the parents/caregivers at Screening, Baseline, and every visit (including Unscheduled Visits that are related to dose change) through the Early Discontinuation/End of Treatment Visit. Preferably, the same parent/caregiver should complete the questionnaires for each visit. The questionnaire will not be collected if the study participant is not living with a parent/caregiver at least part-time, ie, if the parent/caregiver is not able to answer the questions appropriately. The questionnaire should be checked by site personnel for completeness.

11.6 Parent’s Assessment of Arthritis Pain (VAS)

In the Parent’s Assessment of Arthritis Pain (VAS), the parent/caregiver is asked the following question “How much pain do you think your child has had because of his or her illness in the past week?” The parent/caregiver should then place a mark on a 100mm horizontal line to indicate the severity of the pain. This VAS 100mm line has as anchors 0mm representing “No Pain” and 100mm, “Very Severe Pain.”

The Parent’s Assessment of Arthritis Pain (VAS) is provided in Appendix 17.2. The Pain (VAS) will be completed at Screening, Baseline, and every visit through the Early Discontinuation/End of Treatment Visit. Preferably, the same parent/caregiver should complete the scale for each visit. The scale will not be completed if the study participant is not living with a parent/caregiver at least part-time, ie, if the parent/caregiver is not able to answer the question appropriately. The scale should be checked by site personnel for completeness.

11.7 Parent’s Global Assessment of Overall Well-Being (VAS)

In the Parent’s Global Assessment of Overall Well-Being (VAS), the parent/caregiver is asked the following question “Considering all the ways that arthritis affects your child, rate how your child is doing on the following scale by placing a mark on the line.” The parent/caregiver should then place a mark on a 100mm horizontal line ranging from 0 “Very well” to 100 “Very poor.”

The Parent’s Global Assessment of Overall Well-Being (VAS) is provided in Appendix 17.3. The Parent’s Global Assessment of Overall Well-Being (VAS) will be completed at Screening, Baseline, and every visit (including Unscheduled Visits that are related to dose change) through the Early Discontinuation/End of Treatment Visit. Preferably, the same parent/caregiver should complete the scale for each visit. The scale will not be completed if the study participant is not living with a parent/caregiver at least part-time, ie, if the parent/caregiver is not able to answer the question appropriately. The scale should be checked by site personnel for completeness.

11.8 C-reactive protein (CRP)

The acute phase reactant CRP will be analyzed by the central laboratory. Samples will be collected at Screening, Baseline, and every visit (including Unscheduled Visits that are related to dose change) through the Early Discontinuation/End of Treatment Visit. Values

will be used in determining PedACR clinical response, JADAS, CID and CRM, and ratio to Baseline in CRP.

11.9 JADAS

The change in the JADAS from Baseline will be assessed. The JADAS-71 is a composite disease activity score based on a 71-joint count and includes the measures (normalized as needed): Physician's Global Assessment of Disease Activity (VAS) (0 to 10), the Parent's Global Assessment of Overall Well-Being (VAS) (0 to 10), the active joint count (0 to 71), and CRP (0 to 10) (Consolaro et al, 2009; Nordal et al, 2010).

The JADAS will be completed at Screening, Baseline, and every visit through the Early Discontinuation/End of Treatment Visit.

Values of CRP will be normalized to a 0 to 10 scale as follows: if CRP is expressed in mg/dl, any values above 10 are converted to 10. If expressed in mg/L, the value will be first divided by 10 and then any values above 10 will be converted to 10.

Values below the minimum threshold for the method used for CRP determination are converted to 0.

The JADAS is calculated as the linear sum of the scores of the 4 components with a total score range of 0 to 101.

11.10 Clinically Inactive Disease and clinical remission

Criteria for Clinically Inactive Disease (CID) are defined as follows (Wallace et al, 2011):

- No joints with active arthritis*
- No fever, rash, serositis, splenomegaly, or generalized lymphadenopathy attributable to JIA
- No active uveitis as defined by the Standardization of Uveitis Nomenclature Working Group**
- ESR or CRP within normal limits in the laboratory where tested or, if elevated, not attributable to JIA
- Physician's Global Assessment of Disease Activity score of best possible on the scale used (0mm on the 100mm VAS)
- Duration of morning stiffness of ≤ 15 minutes

All criteria must be met.

* Note: The American College of Rheumatology defines a joint with active arthritis as a joint with swelling not due to bony enlargement or, if no swelling is present, limitation of motion accompanied by either pain on motion and/or tenderness. An isolated finding of pain on motion, tenderness, or limitation of motion on joint examination may be present only if explained by either prior damage attributable to arthritis that is now considered inactive or nonrheumatologic reasons, such as trauma.

** Note: The Standardization of Uveitis Nomenclature Working Group defines inactive anterior uveitis as “grade zero cells,” indicating <1 cell in field sizes of 1mm by a 1mm slit beam.

Clinical remission on medication (CRM) is defined as criteria for CID achieved for at least 6 continuous months (Wallace et al, 2004; Wallace et al, 2009).

Clinically Inactive Disease will be assessed at every post-Baseline visit except the Final Visit. Clinical remission on medication will be assessed at every post-Baseline visit from Week 24 onwards, except the Final Visit.

Study participants achieving CRM, ie, after 6 months of continuous CID, may discontinue CZP treatment at the Investigator’s discretion following consultation with the Sponsor to confirm remission status. Study participants who have discontinued CZP due to achieving CRM will be allowed to remain in the study and continue with scheduled study visits. Study participants not maintaining persistent CID following achievement of CRM will be allowed to resume CZP treatment at any time at the Investigator’s discretion and consultation with the Sponsor. If a study participant is on concomitant MTX treatment, the Investigator may decide to decrease and ultimately discontinue the MTX dose after complete discontinuation of CZP. Study participants not maintaining persistent CID following achievement of CRM and resuming treatment will restart the fixed-dose CZP dosing based on their current weight with 3 loading doses of CZP administered Q2W over 6 weeks, followed by a maintenance dose administered Q2W for the duration of the study, with exception of the lowest weight group on the reduced dose regimen, who will receive the maintenance dose Q4W.

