- Percentage of study participants with clinical remission on medication (CRM), as defined in Section 11.10, at every post-Baseline visit from Week 24 onwards except Final Visit.
- Time (in days) to CID.
- Time (in days) to CRM.
- Change from Baseline in DMS at every visit except Final Visit.
- Change from Baseline in FPS-R (child-reported, ages 5 to 11 years), daily during the first week of treatment; Weeks 4, 12, 16, 24, and then every 8 weeks thereafter through the Early Discontinuation/End of Treatment Visit. For study participants enrolled prior to Protocol Amendment 9, visit frequency changes to every 16 weeks instead of every 8 weeks following implementation of Protocol Amendment 8.
- Change from Baseline in JIA Pain VAS, daily during the first 7 days of the study (acute and standard versions); and at Weeks 4, 12, 16, 24, and then every 8 weeks thereafter through the Early Discontinuation/End of Treatment Visit (standard version) for study participants ages 12 to 17 years. For study participants enrolled prior to Protocol Amendment 9, visit frequency changes to every 16 weeks instead of every 8 weeks following implementation of Protocol Amendment 8.
- Change from Baseline in Fatigue Assessment Scale at every visit except Weeks 12 and 20, and Final Visit.

- Juvenile Arthritis School Attendance and Caregiver Work Productivity Survey responses at Baseline, Week 4, and every visit thereafter except Final Visit.

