6 SELECTION AND WITHDRAWAL OF STUDY PARTICIPANTS

6.1 Inclusion criteria

To be eligible to participate in this study, all of the following criteria must be met:

1. An Institutional Review Board (IRB)/Independent Ethics Committee (IEC) approved written Informed Consent form is signed and dated by the study participant or by the parent(s) or legal representative. The Consent form or a specific Assent form, where required, will be signed and dated by minors.
2. Study participant/legal representative/parent is considered reliable and capable of adhering to the protocol, visit schedule or medication intake according to the judgment of the Investigator.
3. Study participant must be able and willing to comply with the requirements of the study.
4. Study participant is 2 to 17 years of age (inclusive) at Baseline (Visit 2).
5. Study participants must weigh ≥ 10 kg (22lb) at Baseline (Visit 2).
6. Study participants must have had onset of signs and symptoms consistent with a diagnosis of JIA (according to the International League of Associations for Rheumatology Classification of Juvenile Idiopathic Arthritis, 2001) and initiation of JIA treatment for at least 6 months prior to Baseline (Visit 2). Eligible JIA categories include: polyarthritis rheumatoid factor-positive, polyarthritis rheumatoid factor-negative, extended oligoarthritis, juvenile psoriatic arthritis, and ERA.
7. Study participants must have active polyarticular-course disease, defined as ≥ 5 joints with active arthritis at Screening and at Baseline.
8. Study participants must have had an inadequate response to, or intolerance to, at least 1 DMARD (nonbiologic or biologic). For example, study participant had prior inadequate response to MTX (based on the Investigator's clinical judgment).
9. If the study participant is using MTX, then the study participant must have been on MTX for a minimum of 3 months at Screening. In addition, the dose must have been stable for at least 1 month before Screening at ≥ 10 to ≤ 15 mg/m² per week. If the study participant is not using MTX, then the treatment must have been previously withdrawn for documented reasons of intolerability or inadequate response.
10. If the study participant is using oral corticosteroid therapy, the dose must have been stable for at least 7 days prior to the Baseline arthritis assessment at a maximum dose of 10mg or 0.2mg/kg prednisone (or equivalent) per day, whichever is the smaller dose.

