8.3 Visits 3 and 4 (Weeks 1 and 2)

- Vital signs (within approximately 15 minutes prior to dosing and [pulse and blood pressure only] approximately 30 minutes after dosing)
- Weight (at Week 2 measurement used to reassess CZP dose according to [Table 7-1](#))
- CRP
- PRINTO/PRCSG standard joint examination
- Physician's Global Assessment of Disease Activity (VAS)
- CHAQ-parent reported
- Parent's Assessment of Arthritis Pain (VAS)
- Parent's Global Assessment of Overall Well-Being (VAS)
- Collection of JIA Pain VAS or FPS-R completed on Day 1 to Day 7
- Clinically Inactive Disease
- DMS
- JADAS
- Fatigue Assessment Scale
- Concomitant medications and procedures
- Adverse events
- IXRS contact
- CZP plasma concentrations (Week 1 only)

- Anti-CZP antibodies (Week 1 only)
- CZP administration (Week 2 only. Self/or parent/caregiver-administration under the supervision of the site staff for training.)

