8.4 Visits 5 to 10 (Weeks 4, 8, 12, 16, 20, and 24)

- Vital signs (within approximately 15 minutes prior to dosing and [pulse and blood pressure only] approximately 30 minutes after dosing)
- Height (Week 24 only)
- Weight (measurement used to reassess CZP dose according to [Table 7-1](#))
- Tanner stages (except growth; Week 24 only)
- Physical examination
- TB questionnaire (study participant and parent/caregiver) (Weeks 12 and 24 only)
- Hematology/biochemistry/urinalysis
- Reproductive potential and birth control
- Pregnancy (urine) test for postmenarcheal females (Weeks 8, 16, and 24 only)
- CRP
- PRINTO/PRCSG standard joint examination
- Physician's Global Assessment of Disease Activity (VAS)
- CHAQ-parent reported
- Parent's Assessment of Arthritis Pain (VAS)
- Parent's Global Assessment of Overall Well-Being (VAS)
- Clinically Inactive Disease
- Clinical remission on medication (at Week 24 only)
- DMS
- JADAS
- FPS-R for study participants ages 5 to 11 years (Weeks 4, 12, 16, and 24 only)
- JIA Pain VAS (standard version, Weeks 4, 12, 16, and 24 only for study participants ages 12 to 17 years)
- Fatigue Assessment Scale (Weeks 4, 8, 16, and 24 only)
- Juvenile Arthritis School Attendance and Caregiver Work Productivity Survey
- Concomitant medications and procedures
- Adverse events
- IXRS contact (Assignment of all required study medication until next scheduled visit.)

- CZP plasma concentrations (predose at Weeks 4, 12, 16, and 24. Study participants will return to the clinic site for a **postdose CZP plasma sample** approximately **5 to 7 days following the Week 16 visit.**)
- Anti-CZP antibodies (predose at Weeks 4, 12, 16, and 24)
- Autoantibodies (ANA and anti-dsDNA antibodies) (Week 16 only)
- CZP administration (At Week 4, self/parent/caregiver-administration under the supervision of the site staff for training. After Week 4, administration of study medication either by site personnel [for those not performing home-based administration] or self/parent/caregiver-administration under supervision of site personnel to ensure proper injection technique.)

Between scheduled visits (Weeks 6, 10, 14, 18, 22, 26, 28, 30), CZP will be administered at home by the study participant or parent/caregiver or study participants may visit the site for CZP administration by staff personnel.

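### CRM is reported from Week 24, when six months of inactive disease cannot yet be documented, and its definition does not exclude visits after CZP has been stopped

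*Protocol*

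**What the plan says.** Section 11.10 gives the definition: "Clinical remission on medication (CRM) is defined as criteria for CID achieved for at least 6 continuous months". The same section fixes the first assessment: "Clinical remission on medication will be assessed at every post-Baseline visit from Week 24 onwards, except the Final Visit". Section 4.3 turns this into an analysis variable, "Percentage of study participants with clinical remission on medication (CRM), as defined in Section 11.10, at every post-Baseline visit from Week 24 onwards", and Section 13.5 repeats it. Table 5-1 footnote p and the Section 8.4 visit list also start CRM at Week 24, and Section 8.5 continues it at every visit from Week 32.

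For the component state, Section 11.10 says: "Clinically Inactive Disease will be assessed at every post-Baseline visit except the Final Visit". Table 5-1 and Section 8.3 put the first such visit at Week 1. Inclusion criterion 7 (Section 6.1) requires at least five "joints with active arthritis at Screening and at Baseline", whereas CID requires none.

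On what follows remission, Sections 7.2 and 11.10 allow CZP to be stopped after six months of continuous CID, at the investigator's discretion and after consulting the sponsor. Then: "Study participants who have discontinued CZP due to achieving CRM will be allowed to remain in the study and continue with scheduled study visits". Section 7.7 confirms that visits go on without dosing, and Sections 7.8.1 and 11.10 allow methotrexate (MTX) to be discontinued afterwards.

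**The concern.** There are two separate problems with one endpoint.

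The first is timing. A state that needs six months to establish is tabulated at a visit before six months of it can have been observed. The Week 24 percentage is then either a structural zero or, if the duration is quietly relaxed in programming (for example by counting from Baseline), a non-zero figure that does not meet the definition. Neither is an efficacy result.

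The second is content. The name says that remission is on medication, but the definition speaks only of how long CID has lasted. A participant who has stopped CZP for CRM, keeps CID and attends scheduled visits still satisfies the wording. Later percentages could therefore pool drug-maintained and drug-free remission under a label that describes only the first.

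**Working it through.** **Inputs**
- CRM duration: at least six continuous months of CID (11.10).
- First CRM visit: Week 24, day 168 (4.3, Table 5-1 footnote p, 8.4, 11.10, 13.5).
- First CID assessment: Week 1, day 7 (Table 5-1, 8.3).
- CID at Baseline: excluded by criterion 7 (6.1).
- Visit window: 3 days either side, relative to Baseline (Section 8).
- Length of six months: not stated. Section 7.8.2 equates four months with 16 weeks; on that usage six months is 6 × 4 × 7 = 168 days. Calendar readings are 181 days (shortest run of six months), 182 days (26 weeks) and 182.6 days (365.25 / 2).

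**Longest documentable CID at Week 24**
- Nominal: 168 − 7 = 161 days.
- Most favourable windows: (168 + 3) − (7 − 3) = 167 days.

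| Reading of six months | Required (days) | Short, nominal | Short, best windows |
|---|---|---|---|
| 24 weeks | 168 | 7 | 1 |
| Shortest calendar six months | 181 | 20 | 14 |
| 26 weeks | 182 | 21 | 15 |
| Half a year | 182.6 | about 22 | about 16 |

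No reading is met. Counting from Baseline would give 168 days, or 171 with the window. That reaches only the 24-week reading, and eligibility rules out CID on that day.

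**First visit at which CRM can be met: Week 32 (day 224)**

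| CID first seen | Days to Week 32 | Meets 168 | Meets 181 to 182.6 |
|---|---|---|---|
| Week 1 | 224 − 7 = 217 | yes | yes |
| Week 2 | 224 − 14 = 210 | yes | yes |
| Week 4 | 224 − 28 = 196 | yes | yes |
| Week 8 | 224 − 56 = 168 | yes, exactly | no |

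The Week 8 row shows why the duration must be stated. With windows, that interval runs from (224 − 3) − (56 + 3) = 162 to (224 + 3) − (56 − 3) = 174 days. It can fall on either side of 168 and never reaches 181. The same choice feeds time to CRM, which is reported in days.

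**Visits after CZP is stopped**

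No arithmetic applies; the sections are set side by side.
1. The definition in 11.10 contains no condition on receiving CZP or any other drug.
2. Participants who stop CZP for CRM continue scheduled visits (7.2, 7.7, 11.10), and CRM is listed at each visit from Week 32 (8.5).
3. Section 13.6 sets non-response for early withdrawal, rescue medication and the pre-visit medication increases listed in 7.8.2, with exceptions after Week 56. Stopping CZP because of CRM is none of these.
4. So a participant off CZP, and possibly off MTX too, who keeps CID still meets CRM as written.

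**The case against.** CRM is neither primary nor secondary. The primary variables are pharmacokinetic, immunological and safety variables, and the secondary ones are Week 16 PedACR responses. A zero one visit too early biases no estimate, and CRM from Week 32 onwards does not depend on the Week 24 row. This stands and limits the weight of the point.

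A reader might infer that the Week 24 interim analysis would show no remission at all. The documents do not support that. Section 13.7 triggers the analysis when active participants complete Week 24, but covers all enrolled participants and does not cut the data at Week 24. Recruitment before Amendment 9 is complete and first visits began in 1Q 2012, so later CRM results should appear beside the zero.

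A reader might also infer that listing CRM at Week 24 opens an early stop of CZP. It does not: Sections 7.2 and 11.10 already require six months of continuous CID and sponsor consultation.

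On the second problem, no sentence says that off-CZP visits count, and Section 13 leaves detail to an analysis plan that is not at hand. Sections 7.2 and 11.10 also speak of maintaining CID after CRM, not of continuing CRM. That is fair, but Sections 4.3 and 13.5 tie the analysis to the Section 11.10 definition, which excludes nothing. Finally, the text does not settle whether medication means CZP alone: a participant off CZP may still take MTX. That defence ends once MTX is stopped too.

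**Conclusion.** The point holds, at modest weight. Under the written definition the Week 24 CRM percentage is 0% by construction, on every reading of six months and with or without visit windows. The shortfall is 1 to 7 days on the 24-week reading and about 14 to 22 days on calendar readings. This assumes that CID duration runs from the first visit at which CID is recorded to the visit being classified.

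The definition also lets off-drug remission enter later CRM percentages. This is a consequence of what the wording leaves out, not an express rule. The documents do not give the number of participants affected, and the analysis plan could already separate them. It would be too strong to say that all later CRM figures are mixed, or that on medication must mean on CZP; the text establishes neither.

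**What to change.** - State six months in days or weeks in Section 11.10, and say how visit windows are treated.
- Start CRM assessment and reporting at Week 32 in Sections 4.3, 8.4, 11.10 and 13.5 and in Table 5-1 footnote p. CID from Week 1, 2 or 4 then qualifies on every reading; CID from Week 8 qualifies only if six months is 168 days.
- State which medication the term on medication refers to.
- Summarise sustained CID after CZP discontinuation separately from CRM while on CZP.

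The cost is wording and one programming flag, with no new data. The Week 24 row is lost, and later CRM percentages may be slightly lower. The change concerns endpoint definition and reporting only and takes no position on when treatment may be stopped.
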